### Study Schema

**List of Abbreviations**

 F-DOPA	3,4-dihydroxy-6-[  F] fluoro-L-phenylalanine
AE	Adverse Event/Adverse Experience
CFR	Code of Federal Regulations
CRF	Case Report Form
CT	Computed Tomography
CTV	Clinical Target Volume
DICOM	Digital Imaging and Communication
DSMB	Data and Safety Monitoring Board
EORTC	European Organization for Research and Treatment of Cancer
FDA	Food and Drug Administration
GCP	Good Clinical Practice
GTV	Gross Tumor Volume
Gy	Gray (radiation dosing)
HIPAA	Health Insurance Portability and Accountability Act
MDASI-BT	MD Anderson Symptom Inventory Brain Tumor Module
MRI	Magnetic Resonance Imaging
NTD	Normal Tissue Dose
IRB	Institutional Review Board
PET	Positron emission tomography
PHI	Protected Health Information
PI	Principal Investigator
PS	Performance Score
PTRAX	Research Participant Tracking System
PTV	Planning target volume
QOL	Quality of Life
RANO	Response Assessment in Neuro-Oncology
RT	Radiation Therapy
RTOG	Radiation Therapy Oncology Group
SAE	Serious Adverse Event/Serious Adverse Experience
SOP	Standard Operating Procedure
T/N	Tumor to normal ratio
UPIRTSO	Unanticipated Problems Involving Risks to Subjects or Others
VEGF-A	Vascular endothelial growth factor- A

## 1.0 Background

Recurrent glioblastoma remains a problem despite modern treatment techniques despite advances in modern therapy; glioblastoma continues to portend a dismal prognosis. In modern trials, median progression-free survival remains short at around 7 months, with nearly all patients experiencing tumor progression by 36 months.[1, 2]

### 1.1 Many recurrences occur outside the high-dose radiotherapy volume:

The current standard for tumor delineation includes T1 contrast-enhanced and T2 FLAIR MRI. It is well established that high-grade gliomas infiltrate into peritumoral edema.[3] In a major prospective trial from the European Organization for Research and Treatment of Cancer (EORTC), the clinical target volume (CTV) included any residual tumor and resection cavity plus 2-cm margins.[4] Current Radiation Therapy Oncology Group (RTOG) protocols include the addition of postoperative edema plus 2-cm margins for CTV.[4] With these volumes, at least 75% of recurrences occur within the 95% isodose line of the 60 Gy volume.[5, 6] In addition, up to 20% of failures are located completely outside of the 95% isodose line.[6]

### 1.2 F-DOPA-PET offers better localization of primary tumor than MRI alone:

While it is well established that regions of contrast enhancement and edema are likely to contain tumor, it is thought that infiltration of tumor may additionally occur along neuronal tracts.[7] Given that up to 20% of patients may experience progression outside the aforementioned MRI changes, a need exists to develop a complementary imaging modality. While standard 18-fluoro-deoxyglucose positron emission tomography (F-FDG-PET) is generally insufficient in visualizing brain tumors, amino acid PET tracers, such as 3,4-dihydroxy-6-[F] fluoro-L-phenylalanine (F-DOPA) offer several advantages.[8] F-DOPA-PET shows high uptake in tumor tissue and low uptake in normal tissue. Unlike contrast enhancement, F-DOPA-PET crosses the intact blood brain barrier freely via an amino acid transporter.[9] In a pilot study at Mayo Clinic, increased F-DOPA-PET uptake was seen in 13 of 16 high-grade biopsy specimens, while MRI T1 contrast enhancement was only present in 6 of the 16 specimens.[10] With this knowledge, Mayo Clinic is currently enrolling patients with newly-diagnosed high-grade gliomas in a radiotherapy trial where dose-escalation is planned for regions of high F-DOPA uptake.

### 1.3 Pseudoprogression can be difficult to differentiate from true tumor progression:

Following treatment with radiotherapy, inflammatory changes are often seen on MRI. Thus, strict criteria are used to categorize the nature of the tumor's response. The historical standard criteria were published by Macdonald et al. and required  $\geq 25\%$  increase in the sum of the products of perpendicular diameters of enhancing lesions, any new lesion, or clinical deterioration in order to declare progression.[11] These

criteria have come into question, as there can be significant interobserver variability, particularly in measuring irregularly shaped or cystic tumors. In addition, changes in contrast enhancement are typically nonspecific and simply represent a disrupted blood-brain barrier. Thus, fluctuations in contrast enhancement may be caused by inflammatory changes in the treated region, anti-angiogenic agents and radiation necrosis.[12] Pseudoprogression, defined as an increase in contrast enhancement that subsides without anti-neoplastic therapy, is common after standard treatment with radiotherapy and temozolomide.[13] This process is thought to be driven by radiation-induced increased permeability of the blood brain barrier. Because pseudoprogression typically occurs within 12 weeks of radiotherapy inside the high-dose region, the updated Response Assessment in Neuro-Oncology (RANO) criteria require new enhancement outside the 80% isodose line or viable tumor on histopathologic sampling for progression to be declared less than 12 weeks after radiotherapy.[14] These criteria help differentiate pseudoprogression from true progression, though challenges in interpreting changes in imaging after 12 weeks still remain.

#### 1.4 Bevacizumab produces a moderately high response rate in glioblastoma:

While angiogenesis is common among a spectrum of tumors, it is particularly frequent in glioblastoma. Commonly, the tumor parenchyma produces vascular endothelial growth factor A (VEGF-A), which in turn up-regulates the VEGF pathway.[4] Bevacizumab is a humanized monoclonal antibody with activity against the VEGF-A ligand, which in turn reduces VEGF pathway up-regulation.[15] A randomized study comparing bevacizumab with or without irinotecan in patients with recurrent glioblastoma demonstrated moderately high response rates in the 30-35% range as determined by MRI.[16] A single-arm phase II study treating recurrent glioblastoma with bevacizumab followed by bevacizumab and irinotecan after further progression produced a response rate of 35% as defined by Macdonald criteria.[17] These trials led to FDA approval for bevacizumab use in the treatment of recurrent glioblastoma. This led to RTOG 0825, a randomized placebo-controlled trial comparing standard radiotherapy and temozolomide with or without adjuvant bevacizumab. This study revealed an improvement in progression-free survival but not overall survival.[4] A subsequent study compared concurrent radiotherapy, temozolomide and bevacizumab to radiotherapy and temozolomide alone, demonstrating a similar improvement in progression-free but not overall survival.[18] Responses were often measured radiographically, which may not be the most reliable indicator of response to anti-angiogenic agents.

#### 1.5 MRI changes after bevacizumab may not accurately reflect tumor response:

While rapid responses in MRI contrast enhancement after initiation of treatment with VEGF pathway inhibitors are relatively common, it is not clear whether these changes truly reflect tumor regression or simply restoration of the blood-brain barrier.[19] Furthermore, increasing non-enhancing T2 FLAIR regions have been reported and may potentially represent tumor progression after bevacizumab.[20] This has driven

speculation that the improvement in progression-free but not overall survival with bevacizumab may be primarily driven by radiographic changes that do not fully correlate with true tumor response.

#### 1.6 Reirradiation is often used for treatment of progression:

Repeat courses of radiotherapy are often considered for progressive disease refractory to systemic therapy. Conventionally fractionated doses between 36 and 46 Gy have been used with minimal neurologic toxicity.[21-23] Hypofractionated doses of 24-50 Gy in 3.5-5 Gy fractions have also been used with minimal toxicity when limiting doses to <40 Gy.[22, 24-29] Mayer and colleagues proposed a cumulative normal tissue dose limit (2 Gy per fraction equivalent) of <100 Gy to limit the risk of radionecrosis.[30] In general, the target volume includes a minimal expansion beyond MRI contrast enhancement.[21, 24-27, 29] Median survival after reirradiation ranges from 7 to 10 months.[21-27, 29] The best outcomes are seen when more time elapses between primary radiation and reirradiation and in patients with lower-grade histology.[24-26, 31] In an analysis of patterns of recurrence after reirradiation, 60-70% recurrences were located in-field with the remainder located out of field.[25, 32] Thus, MRI contrast enhancement may not accurately reflect tumor location potentially resulting in imprecise targeting of radiation target volumes.

#### 1.7 $^{18}\text{F}$ -DOPA-PET may allow better localization of recurrent disease than MRI:

Because of the shortcomings of MRI in accurately differentiating tumor progression from pseudoprogression, in addition to the difficulty in truly assessing the response to bevacizumab, a novel imaging modality would prove useful in accurately classifying responses to treatment. In addition, more precise target delineation in the re-irradiation setting is particularly attractive; so as to allow for not only better target coverage but potentially reduced unnecessary coverage of normal tissue. The lack of dependence of  $^{18}\text{F}$ -FDOPA-PET uptake on blood-brain barrier breakdown is enticing, as many of these patients are currently receiving or recently received bevacizumab and may have alterations in the blood-brain barrier.

1.71 Preliminary results –  $^{18}\text{F}$ -DOPA-PET identifies glioma outside conventional MRI in patients with imaging findings consistent with recurrent disease. In our two studies (MC1078 and MC1373), 13 patients with suspected recurrent disease had an  $^{18}\text{F}$ -DOPA-PET/CT scan and MRI performed prior to stereotactic resection or biopsy. The PET scan was rigidly registered to the T1-weight scan using MIM Maestro (MIM Software Inc, Cleveland, OH). The registered PET images were transferred to the Stealth Station Neuronavigation System (Medtronic Sofamor Danek, Memphis, TN) and stereotactic biopsy locations were planned based on the PET SUVmax and locations of PET and MRI discordance (Figure 1). Of 45 biopsy specimens graded by Dr.

[figure not shown]

Figure 1.  $^{18}\text{F}$ -DOPA-PET fused with T1-post contrast MRI in a patient with recurrent high-grade glioma. Note  $^{18}\text{F}$ -DOPA avidity outside region of MRI contrast enhancement.

[name], 39 contained tumor. Fifteen samples were taken in regions of  $^{18}\text{F}$ -DOPA avidity in the absence of MRI contrast enhancement (M-P+). Of these, 14 (93%) contained tumor and 10 (66%) were high-grade. Of the 33 specimens containing high-grade glioma, 20 (61%) were from regions of MRI contrast enhancement and 26 (79%) were from regions of  $^{18}\text{F}$ -DOPA avidity.

## 2.0 Goals

### 2.1 Primary

- 2.11 Compare the progression-free survival rate at 3 months for recurrent high-grade glioma patients after reirradiation targeting volumes designed with both  $^{18}\text{F}$ -DOPA-PET and conventional MRI with historical controls

### 2.2 Secondary

- 2.21 Compare overall survival from reirradiation and overall survival from initial diagnosis with historical controls
- 2.22 Prospectively evaluate toxicity and reoperation rates after reirradiation
- 2.23 Prospectively evaluate quality of life and fatigue using patient reported outcomes

### 2.3 Correlative Research

- 2.31 Compare volume of  $^{18}\text{F}$ -DOPA-PET uptake with MRI contrast enhancement and T2 FLAIR for patients undergoing re-irradiation for recurrent high-grade glioma
- 2.32 Evaluate patterns of failure after reirradiation in relation to pre-treatment MRI and  $^{18}\text{F}$ -DOPA-PET abnormalities

### 3.0 Patient Eligibility

#### 3.1 Inclusion Criteria

- 3.11 Age  $\geq$  18 years
- 3.12 ECOG PS  $\leq$  3
- 3.13 Histologically confirmed or radiographic evidence of recurrent/progressive glioma
- 3.14 History of radiation therapy to the brain for prior diagnosis of glioma
- 3.15 Planned radiation treatments at Mayo Clinic Rochester
- 3.16 Provide informed written consent
- 3.17 Willing to sign consent onto the Mayo Clinic Radiotherapy Patient Outcomes Registry and Biobanking study, IRB number 15-000136 (blood draw optional)
- 3.18 Willing to return to enrolling institution for follow-up during Active Monitoring Phase of the study.

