**12.0 Descriptive Factors**

- Corticosteroid therapy at study entry: yes (specify dose) vs no
- Histologic grade of primary tumor: 3 vs 4
- Histologic type of primary tumor: oligodendroglioma vs oligoastrocytoma vs astrocytoma vs other (specify)
- ECOG PS (see Appendix I): 0 vs 1 vs 2 vs 3
- Neurologic deficit: yes (specify) vs no
- History of seizures: yes (specify last seizure) vs no
- Prior surgical resection or biopsy: yes vs no
- Age:  $\leq 70$  vs  $> 70$
- MGMT: methylated vs unmethylated vs not available
- IDH status: mutated vs wild type vs not available
- 1p/19q status: single deleted vs codeleted vs not available
- Time since last RT course:  $< 6$  months vs 6-12 months vs  $> 12$  months
- Salvage chemotherapy: yes (specify agents, dates treated) vs no

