## 16.0 Statistical Considerations and Methodology

### 16.1 Study Overview

This is a single-arm, single-stage phase II Simon's Optimum study with an analysis that will compare progression-free survival (PFS) at 3 months for recurrent glioma patients after radiotherapy targeting volumes designed with both F-DOPA-PET and MRI information with historical controls.

16.11 The primary endpoint of this trial is the proportion of patients that experience progression-free survival at 3 months based on our hypothesis that the combination of more accurate target delineation of high-grade glioma by F-DOPA-PET will improve overall tumor control.

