### 16.2 Statistical Design

#### 16.21 Decision Rules

The primary endpoint of this trial is the proportion of patients treated with F-DOPA-PET guided radiotherapy who are alive and have not progressed within 3 months. A success will be a patient who is alive and without evidence of progressive disease within 3 months from registration. Median PFS after bevacizumab failure ranges between 1-2 months.[17, 34] Thus, the largest success proportion where the proposed treatment would be considered ineffective in this population is 20%. The following Simon's Optimum design uses 20 patients to test the null hypothesis that the proportion of successes is at most 20% with an overall significance level (alpha) of 0.186, and a power of 85.9% to detect a true success proportion of 40%.

16.22 After 10 evaluable patients are accrued to this study and followed for at least 3 months, if 2 or more successes are alive and progression-free at 3 months, the results will wait until conclusion of the study. If 1 or fewer patients are alive without evidence of progression at 3 months, the study will be stopped and the treatment will be deemed ineffective in this population.

16.23 After 20 evaluable patients are accrued to this study and followed for at least 3 months, if 6 or more successes are observed we may recommend further testing of this regimen in subsequent studies in this patient population.

16.24 We will not suspend accrual between stages to allow the first 20 patients to become evaluable, unless undue toxicity is observed.

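### Eligibility and the primary test admit recurrent glioma of any grade, although the question is about high-grade disease and the 20% null comes from bevacizumab-failed glioblastoma; lower-grade entrants would bias the go decision upward by an unknown amount.

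*Combined protocol and SAP*

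**What the plan says.** Section 3.1 sets the disease criteria: "Histologically confirmed or radiographic evidence of recurrent/progressive glioma" (3.13) and "History of radiation therapy to the brain for prior diagnosis of glioma" (3.14). No exclusion in 3.2 refers to grade. Under 16.711, every eligible, consented patient who begins guided reirradiation at the institution is evaluable for the primary endpoint.

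The question is narrower. Goal 2.11 is to "Compare the progression-free survival rate at 3 months for recurrent high-grade glioma patients" treated this way with historical controls. Correlative goal 2.31, the hypothesis in 16.11, and endpoints 16.84 and 16.85 also refer to high-grade glioma. Section 16.1, however, says the analysis will "compare progression-free survival (PFS) at 3 months for recurrent glioma patients", with no grade.

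The null is narrower still. Section 16.21 derives 20% from this statement: "Median PFS after bevacizumab failure ranges between 1-2 months". It cites references 17 and 34, both titled as studies of recurrent glioblastoma.

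On prognosis, Section 1.6 states: "The best outcomes are seen when more time elapses between primary radiation and reirradiation and in patients with lower-grade histology". Section 12.0 records "Histologic grade of primary tumor: 3 vs 4" as a descriptive factor. Section 5.0 has no stratification, and 16.7 does not name grade among its example subgroup factors.

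**The concern.** A single-arm test against a fixed proportion is only as good as the match between the patients counted and the null. As written, a patient with a grade 2 recurrence is eligible, evaluable and counted toward the 6 successes in 20, although that patient lies outside the stated question and outside the population that gave the 20%. Because the protocol itself says lower-grade disease does better after reirradiation, the bias runs toward a go.

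Nothing later in the plan corrects this. The decision rule ignores case mix, and the grade item in 12.0 has no category in which a grade 2 primary could be recorded. With 20 patients and a declared alpha of 0.186, there is little room for case mix to act in the same direction as a treatment effect.

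**Working it through.** **Inputs from the documents.** Null 0.20, alternative 0.40, alpha 0.186 and power 85.9% (16.21). Stage 1: 10 patients, stop at 1 or fewer successes (16.22). Final: 20 patients, go at 6 or more successes (16.23).

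**Inputs assumed.** The share f of lower-grade patients (5-30%) and their 3-month PFS without any treatment effect, q (40-80%). The documents give no figure for either.

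**Step 1: reproduce the plan's figures.** With X1 successes in the first 10 and X2 in the next 10,

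P(go) = sum over x = 2 to 10 of P(X1 = x) × P(X2 ≥ 6 − x).

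At p = 0.20:

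- x = 2: 0.3020 × 0.1209 = 0.0365
- x = 3: 0.2013 × 0.3222 = 0.0649
- x = 4: 0.0881 × 0.6242 = 0.0550
- x = 5: 0.0264 × 0.8926 = 0.0236
- x ≥ 6: 0.0064 × 1 = 0.0064

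The sum is 0.1863 (from unrounded terms), which matches 0.186. The same formula at p = 0.40 gives 0.8586, which matches 85.9%.

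**Step 2: let case mix act alone.** Hold high-grade patients at 0.20 and give no one a treatment effect. The success rate of the mix is p = (1 − f) × 0.20 + f × q. For example, f = 0.10 and q = 0.60 give 0.18 + 0.06 = 0.24; f = 0.30 and q = 0.80 give 0.14 + 0.24 = 0.38. P(go) at the resulting p:

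| Assumed share f | q = 40% | q = 60% | q = 80% |
|---|---|---|---|
| 5% | 0.219 (p = 0.21) | 0.254 (p = 0.22) | 0.290 (p = 0.23) |
| 10% | 0.254 (p = 0.22) | 0.328 (p = 0.24) | 0.407 (p = 0.26) |
| 20% | 0.328 (p = 0.24) | 0.486 (p = 0.28) | 0.637 (p = 0.32) |
| 30% | 0.407 (p = 0.26) | 0.637 (p = 0.32) | 0.816 (p = 0.38) |

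The table treats each entrant's grade as a random draw. Fixing the number of lower-grade patients among the 20, in random order, changes little: 2 patients at q = 60% give 0.322 and 4 give 0.488.

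**Step 3: how firmly the source supports 20%.** If PFS is exponential (an assumption), 3-month PFS = 0.5^(3/median). A median of 1 month gives 12.5%, a median of 2 months gives 35.4%, and 20% corresponds to a median of 1.29 months. At p = 0.354, P(go) is 0.747. So 0.186 depends on the choice of null even in the source population.

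**The case against.** High-grade disease was plainly intended. Goals 2.11 and 2.31, the 16.11 hypothesis, 16.84 and 16.85 all say so, and the 3 vs 4 item in 12.0 suggests that few or no grade 2 primaries were expected. The gap may be a wording slip. Sections 16.7 and 16.8 plan subgroup analyses by known prognostic factors, and the list in 16.7 is only illustrative, so case mix could be reported. A go means only that further testing may be recommended, at a declared alpha of 0.186.

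Much of this stands. Intent is visible, and the consequence is conditional on who enrols. But enrolment and evaluability follow 3.13, 3.14 and 16.711, not intent. A descriptive factor restricts nothing, and a subgroup report does not change the count of successes.

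Three stronger readings are tempting, and the documents support none of them:

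- A reader might take the upper end of the table as the likely error rate. The documents give no share and no PFS for lower-grade patients, and mild assumptions (5-10% at 40%) give only 0.22-0.25.
- A reader might take Section 1.6 as a statement about grade 2. Its wording is relative and could mean grade 3 against grade 4. It supports the direction of the bias, not a rate.
- A reader might infer that a grade 3-4 restriction secures the 0.186. It does not. The null comes from glioblastoma after bevacizumab failure, while grade 3 is anticipated in 12.0 and bevacizumab failure is not an entry criterion.

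**Conclusion.** The inconsistency is in the text and is certain: any-grade eligibility and evaluability sit beside a high-grade question and a null from bevacizumab-failed glioblastoma. The direction of the bias, toward a go, follows from Section 1.6. Its size is unknown. Over assumed shares of 5-30% and 3-month PFS of 40-80%, with high-grade patients exactly at 20% and no treatment effect, the chance of a go is about 0.22 to 0.82 instead of 0.186. These figures show sensitivity and are not a forecast; if no lower-grade patient enrols, this particular bias is zero. The mismatch with the null for grade 3 and bevacizumab-naive patients would remain even then. The wording should be corrected because this is the trial's one formal decision and the change is small.

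**What to change.** Choose one of two changes.

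1. Amend 3.13 to require high-grade (grade 3-4) glioma. State whether grade is taken from the primary tumor or from the latest histology, and what applies when recurrence is shown only radiographically. Align 12.0 and 16.1 with that choice. At present 12.0 records the primary tumor only, so a grade 2 primary that has transformed would have no category.
2. Keep any-grade entry, but restrict the evaluable set in 16.711 and the counts in 16.22 and 16.23 to grade 3-4, and report other patients descriptively. Add a category below grade 3 to 12.0.

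With either change, state in 16.2 that the 0.186 error rate holds only if 20% is the right null for the patients tested, because grade 3 and bevacizumab-naive patients remain eligible. Add grade and prior bevacizumab to 16.7 as factors by which the primary proportion is reported. The salvage-chemotherapy item in 12.0 already asks for agents and could be worded to make sure bevacizumab is captured.

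Cost: wording, and somewhat slower accrual. The target of 20 evaluable patients and the cut-offs stay. Section 16.4 needs 10 of about 25 recurrent glioma patients a year (10/25 = 40%); the high-grade share of those 25 is not stated, so the remaining margin cannot be computed. Under the second option, the allowance in 16.3 (22 − 20 = 2 patients) would also have to cover lower-grade entrants and may need to rise.

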#### 3.2 Exclusion Criteria

- 3.21 More than one prior course of radiotherapy or prior prescription doses exceeding 60 Gy to re-irradiation target volumes
- 3.22 Unable to undergo MRI scans with contrast
- 3.23 Unable to undergo an  $^{18}\text{F}$ -DOPA-PET scan (e.g., Parkinson's Disease, taking anti dopaminergic, or dopamine agonist medication or less than 6 half-lives from discontinuance of dopamine agonists.)

Note: Other potentially interfering drugs: amoxapine, amphetamine, benztropine, bupropion, buspirone, cocaine, mazindol, methamphetamine, methylphenidate, norephedrine, phentermine, phenylpropanolamine, selegiline, paroxetine, citalopram, and sertraline). If a patient is on any of these drugs, list which ones on the On-Study form.

- 3.24 Any of the following:
  - Pregnant women
  - Nursing women
  - Men or women of childbearing potential who are unwilling to employ adequate contraception

